12 MAY 2021

PROTOCOL NUMBER 2020089

PII

2020089

Table of Contents

1.	Title Page.....	1
2.	STUDY OBJECTIVE.....	3
3.	OVERALL STUDY DESIGN AND PLAN	3
4.	INCLUSION CRITERIA	5
5.	EXCLUSION CRITERIA.....	5
6.	CONTINUANCE CRITERIA	5
7.	IDENTITY OF INVESTIGATIONAL AND ACCLIMATION PRODUCT(S).....	5
8.	PRODUCT USAGE.....	5
9.	BLINDING, LABELING, AND SHIPPING PLAN	6
10.	METHOD OF ASSIGNING SUBJECTS TO TREATMENT GROUPS.....	6
11.	DETERMINATION OF SAMPLE SIZE	6
12.	SAFETY VARIABLES	6
13.	EFFICACY VARIABLE	7
14.	HYPOTHESES	8
	STATISTICAL AND ANALYTICAL PLANS	9
	APPENDIX.....	10

List of Abbreviations and Definition of Terms

Abbreviation	Definition
ADA	American Dental Association
AE	Adverse Event
CFR	Code of Federal Regulations
CRF(s)	Case Report Form(s)
FDA	Food and Drug Administration
GCP	Good Clinical Practices
IRB/IEC	Institutional Review Board/Independent Ethics Committee
OST	Oral Soft Tissue Exam
SOP	Standard Operating Procedure

2020089

1. Study Objective

The objective of this pilot study is to evaluate the effectiveness of denture gel at treating and preventing gum abrasions while eating peanuts.

2. Overall Study Design and Plan

This is a single center, two-treatment, parallel design study. Up to 40 subjects will be enrolled with a full mandibular and full maxillary denture with a history of food related abrasions.

At each visit, an Oral Soft Tissue exam, a Mucosa Condition Assessment and a Gum Abrasion Evaluation will be performed. At Baseline, the subjects will be randomized to a treatment group. At Baseline, Week 2, and Week 4 subjects will be asked to eat 20 grams of peanuts 4 times for a total consumption of 80 g of peanuts (subjects will be permitted to take breaks if needed and drink small sips of water). Following the peanut challenge, a licensed dental professional will re-evaluate the number and size of abrasions. Subjects will receive a consumer questionnaire to complete as well prior to the Baseline, Week 2, and Week 4 assessments.

Table 1. Study Schedule by Procedure Type and Visit

PROCEDURE	BASELINE	DAYS 3, 6	WEEK 2	WEEK 4
Informed Consent	X			
Medical History Review	X			
Demographics	X			
Inclusion/Exclusion Criteria	X			
Randomization	X			
Continuance Criteria		X	X	X
OST	X	X	X	X
Mucosa Condition Assessment	X	X	X	X
Pre-Peanut Gum Abrasion Evaluation	X	X	X	X
Product distribution/instruction	X			
Subject eats 80 g of peanuts (20g, 4 times)	X		X	X
Post-Peanut Gum Abrasion Evaluation	X		X	X
Questionnaire*			X	X

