General Comments	X	X	X	X
AEs	X	X	X	X
Subject Accountability				X**

*This questionnaire will be analyzed outside of this protocol.

**Subject accountability will be completed after subjects complete the study at any time.

2020089

Prior to the Baseline, subjects will be asked to refrain from eating approximately 4 hours prior to their appointment. Previously screened subjects will review and sign an informed consent and receive a copy at the Baseline visit. The subjects' medical history will be collected or updated on site source documents. Demographic information and Inclusion/Exclusion Criteria will be obtained and documented on the appropriate case report form (CRF).

Subjects will be asked to remove their mandibular and maxillary full dentures and the dentures will be cleaned (if applicable) and examined by a dental professional. An OST will be performed followed by a Mucosa Condition Assessment, and a baseline pre-peanut challenge Gum Abrasion Evaluation.

Subjects will be asked to eat 20 grams of peanuts 4 times for a total consumption of 80 g of peanuts (subjects will be permitted to take breaks if needed and drink small sips of water). Additionally, subjects will be timed for each peanut challenge. If subjects are unable to finish the peanuts due to being too full or for any other reason, this will be noted in the eCRF General Comments. After completion of the peanut challenge, subjects will have a post-peanut challenge Gum Abrasion Evaluation.

Next subjects will be randomized to one of two treatments balanced on their baseline post-peanut challenge gum abrasion evaluations (area and number) mucosa condition, and age. The subjects will receive their products and site staff will review and provide written product use instructions.

Subjects will be reminded to refrain from eating approximately 4 hours prior to next visit.

Day 3, 6

Continuance criteria will be assessed. Subjects will be asked to remove their mandibular and maxillary full dentures and the dentures and subjects' mouths will be cleaned by a dental professional if applicable. An OST will be performed followed by a Mucosa Condition Assessment and then a Gum Abrasion Evaluation. Subjects will be reminded to refrain from eating approximately 4 hours prior to next visit.

Week 2

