In the evening subjects will perform their regular denture cleaning routine. They will be instructed to sleep without dentures.

Evening gel application:

Subjects will rinse out their mouth with water (if subjects brush their oral mucosa with brush, they will be allowed to continue doing so) and apply gel to their mucosa where they normally wear upper or lower denture.

Subjects will apply gel in the following order, reapplying gel onto the applicator each time:

- onto the mucosa (right half) under the upper denture
- onto the mucosa (left half) under the upper denture
- onto the mucosa (right half) under the lower denture
- onto the mucosa (left half) under the lower denture

Subjects will leave the gel overnight.

Subjects will not eat or drink anything in the evening after applying the gel.

8. Blinding, Labeling, and Shipping Plan

The take home kit boxes for the Control Group will contain a subject instruction sheet. The take home kit boxes for the Treatment Group will contain disguised and labeled gel, an applicator, and a subject instruction sheet. All instructions will be given (written and verbal). All labels will contain the study number, emergency phone number, distributor name/address, appropriate caution statements, and other information as required by internal regulations and clinical Standard Operating Procedures (SOPs). The shipping containers will be labeled with the "ship to" clinical site address and a "content statement" listing study number and number of kit boxes contained within. Supplemental product will be provided to the site.

9. Method of Assigning Subjects to Treatment Groups

Subjects who meet enrollment criteria will be stratified based on Baseline post-challenge number of lesions (< 1.6 vs. \geq 1.6), size of lesion (<16mm vs \geq 16mm), mucosa condition (\leq 1 vs. \geq 1), and age (\leq 64 vs. $>$ 64).

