Subjects will then be randomized to one of the two (2) treatment groups using a balance and assignment procedure on site. This assignment process and the distribution of test products will be conducted in a protected area that will ensure blinding of the examiner to the identity of the test products. Product will be distributed according to a randomization schedule provided by the Sponsor. Product distribution and product return will be recorded on the Clinical Materials Inventory provided by the Sponsor. Subjects from the same household will be assigned to the same treatment group. The balance and assignment cut points may be adjusted during the study.

10. Determination of Sample Size

The sample size of 40 subjects was chosen for logistical reasons.

11. Safety Variables

Safety Observations and/or Measurements

Safety will be assessed by the absence of irreversible side effects.

Oral Examination

2020089

Assessment of the oral soft tissue is conducted via a visual examination of the oral cavity and perioral area utilizing a standard dental light, dental mirror, and gauze. The structures examined include the ridge, hard and soft palate, oropharynx/uvula, buccal mucosa, tongue, floor of the mouth, labial mucosa, mucobuccal/mucolabial folds, lips, and perioral area. All abnormal findings will be recorded and categorized by their location. An AE will be recorded if a new abnormal finding is noted after product distribution or any previously noted abnormal finding increases in severity during the treatment period. Subjects who experience an AE may be examined by the Medical Monitor, if necessary.

12. Efficacy Variable

Gum Abrasion Evaluation:

A dental professional will assess the gingiva for any gum abrasions. A periodontal probe will be used to measure the size of any presenting abrasions and will be documented in the eCRF. The gum abrasion will continue to be measured throughout the duration of the study to track healing of the abrasion.

Staining Procedure

Staining solution: Mira-2-Ton (Mira-2-Ton® Hager & Werken GmbH & Co. KG. Duisburg, Germany) – same batch of stain solution will be used through the whole study.

[figure not shown]
Prior to the staining oral mucosa will be dried with the air blast. Subjects will swish 5 mL of Mira-2-Ton dye for 10 seconds followed by 5 mL of water for 10 seconds as well.

Abrasion assessment

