Prior to the assessment, the mucosa under the denture will be dried with the air blast. During the measurement, the size of each lesion (colored dark blue) will be measured using periodontal probe (assessing the length and width of the lesion). The location of the lesion(s) will also be documented on the diagram below, including whether the lesion is on the ridge or the mucosa (Pre-challenge Abrasion Evaluation). The assessment notes on Figure 1 below will be summarized into ECRF. All abrasion assessments will be carried out in the same quadrant ordering. Loosely attached discolorations will be excluded from evaluation. If examiner has difficulty with assessment (plaque or abrasion), she/he will carefully try to remove the staining (non-removable stains will be assessed as abrasion). After the peanut eating exercise (no adhesive period), subjects will be instructed to rinse out their mouth till all of the particles are removed and the oral mucosa under the denture will be re-stained again prior to the 2nd assessment (Post-challenge Abrasion Evaluation).

Figure 1 _ The location (and shape) of each gingival abrasion would be drawn on a maxillary and mandibular denture ridge chart.

2020089

The exact dimension (as measured with the periodontal probe) of the abrasion will be recorded. For analysis purposes, abrasion might be divided into the following categories:

- small, if $\emptyset \leq 2.5$ mm,
- medium, if $\emptyset > 2.5$, but ≤ 5 mm,
- large, if $\emptyset > 5$ mm.

Images (traditional or 3D) of abrasions might be taken for documentation and exploratory purposes.

Mucosa Condition Assessment:

The entire mucosal region under the denture will be assessed with one score per arch.

0 = pink firm tissue absent of redness and inflammation; 1 = mild redness or inflammation – slight change in color and little change in texture; 2 = moderate redness and/or inflammation – moderate glazing, redness, edema and hypertrophy 3 = severe redness and/or inflammation – marked redness and hypertrophy

13. Hypotheses

Treatment

Null Hypothesis: There is no difference between treatment groups for the abrasion endpoints (number of abrasions and size of abrasions, and mucosa assessment) across first 7 days after adjusting for the respective Baseline visit post-challenge abrasion endpoint.

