Alternative Hypothesis: There is a difference between treatment groups in abrasion endpoints (number of abrasions and size of abrasions, and mucosa assessment) across first 7 days after adjusting for the respective Baseline visit post-challenge abrasion endpoint.

Prevention

Null Hypothesis: There is no difference between treatment groups for the abrasion endpoints (number of abrasions and size of abrasions, and mucosa assessment) across weeks 2 and 4 after adjusting for the respective Baseline visit post-challenge abrasion endpoint.

2020089

Alternative Hypothesis: There is a difference between treatment groups in abrasion endpoints (number of abrasions and size of abrasions, and mucosa assessment) across weeks 2 and 4 after adjusting for the respective Baseline visit post-challenge abrasion endpoint.

14. Statistical and Analytical Plans

To assess the impact of the product on the treatment of lesions, the average size of the Pre-challenge Abrasions (in mm) and the average Number of Pre-challenge Abrasions, and Mucosa Assessment across days 3 and 6 will be analyzed using a repeated measures analysis of covariance with factors in the analysis for treatment, day and respective baseline post-challenge lesion variable as the covariate. The treatment by baseline lesion and treatment by day interactions will be assessed at the 10% level. Additionally, the by day responses will also be carried out separately from the repeated measures model,

To assess the impact of the product on the prevention of lesions, the average size of the Pre-challenge Abrasions (in mm), the average Number of Pre-challenge Abrasions, and Mucosa Assessment across weeks 2 and 4 will be analyzed using a repeated measures analysis of covariance with factors in the analysis for treatment, week and respective baseline post-challenge lesion variable as the covariate. The treatment by baseline lesion and treatment by week interactions will be assessed at the 10% level. Additionally, the by week responses will also be carried out separately from the repeated measures model,

The size of the Pre-challenge Abrasions might be collapsed into pre-defined categories.

Additional analysis of the data might be carried out for exploratory purposes. If the data does not satisfy the normality assumption, then a non-parametric analysis will be utilized. All statistical tests will be two-sided with 10% Type I error rate.

Demographic data will be summarized for all subjects randomized in the study.

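### Allocation is balanced on four baseline variables but each Section 14 model adjusts for only one of them, which forgoes some precision if the other three are prognostic (minor)

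*Combined protocol and SAP*

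**What the plan says.** Section 2 has subjects "randomized to one of two treatments balanced on their baseline post-peanut challenge gum abrasion evaluations (area and number) mucosa condition, and age". Section 9 repeats the four variables with cut points: "Subjects who meet enrollment criteria will be stratified based on Baseline post-challenge number of lesions", then lesion size (called area in Section 2), mucosa condition and age. It does not describe the balancing algorithm, and it lets the cut points change during the study. It also sends members of one household to the same arm.

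Section 14 gives two repeated measures ANCOVAs. The treatment question (days 3 and 6) has "factors in the analysis for treatment, day and respective baseline post-challenge lesion variable as the covariate". The prevention question (weeks 2 and 4) has "factors in the analysis for treatment, week and respective baseline post-challenge lesion variable as the covariate". The Section 13 hypotheses use the same adjustment, for example "across first 7 days after adjusting for the respective Baseline visit post-challenge abrasion endpoint". The interactions to be assessed bring in no further balancing variable. The fallback names no method and no covariates: "If the data does not satisfy the normality assumption, then a non-parametric analysis will be utilized". Tests are two-sided at 10%.

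On size, Section 2 says "Up to 40 subjects will be enrolled" and Section 10 says "The sample size of 40 subjects was chosen for logistical reasons". No section explains why the other balancing variables are left out or plans a sensitivity analysis that includes them. Section 14 allows only unspecified exploratory work.

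**The concern.** Balancing on a prognostic variable makes the arms more alike than chance would, so the treatment estimate varies less from trial to trial. A model that omits the variable leaves its contribution in the residual, and the reported standard error does not reflect the gain. Two things follow if the omitted variables matter. The test runs below its nominal level, and power that the collected data could supply is not used. With at most 40 subjects and a size fixed by logistics, extra precision has to come from the analysis.

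**Working it through.** **1. No figure in the plan to reproduce.** The documents give N up to 40 and a two-sided 10% level. They give no power, effect size, SD, dropout rate, allocation ratio or prognostic strength. Assumed here: 1:1 allocation, 20 per arm.

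**2. Balanced on against adjusted for.**

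| Model | Baseline covariate in Section 14 | Balancing variables left out |
|---|---|---|
| Lesion number | number | size, mucosa, age |
| Lesion size | size | number, mucosa, age |
| Mucosa | mucosa (natural reading) | number, size, age |

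The mucosa row needs interpretation. Section 14 asks for a post-challenge baseline lesion variable, but the schedule and visit text place the mucosa assessment before the challenge only. If a lesion variable were meant, three of the four would still be missing.

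**3. Approximation.** Let σ be the SD left after own-baseline adjustment, and R2 the share of that variance explained by the three omitted variables.

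- Planned SE = σ√(2/20) = 0.316σ.
- With perfect balance, the true SD of the estimate is 0.316σ√(1−R2).
- Actual level of the planned test = 2[1 − Φ(1.645/√(1−R2))]: 8.3%, 6.6% and 4.9% at R2 = 10%, 20% and 30%.

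These are lower limits, because balancing on dichotomised variables in 40 subjects is imperfect.

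- Unadjusted power for 0.6σ = Φ(0.6/0.316 − 1.645) = Φ(0.25), about 60%.
- At R2 = 30% with full adjustment, the SE is 0.265σ and power is Φ(0.6/0.265 − 1.645) = Φ(0.62), about 73%, before the loss of degrees of freedom.

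**4. Simulation.** There were 20,000 runs per setting (Monte Carlo SE about 0.2 points on type I error). Allocation was by minimisation on four binary factors with probability 0.8 (an assumption). Outcomes were subject means over two visits: normal, count, right-skewed size, and 0-3 ordinal. Completers were 40 or 34. No households were simulated.

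| R2 | Type I error, planned | Power change from adding the three (0.6 SD) |
|---|---|---|
| 0 | 9.5-10.1% | −1.1 to −2.9 points |
| 10% | 8.7-9.4% | +0.4 to +3.0 |
| 20% | 7.3-8.9% | +2.8 to +7.2 |
| 30% | 6.4-7.9% | +4.8 to +11.8 |

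- With all four variables in the model, type I error is 9.2-10.4% throughout.
- Interpolating the power change between R2 = 0 and 10% puts break-even at about 3-9%.
- For a normal outcome with 40 completers and R2 = 30%, power goes from 60% to 71%, just under the 73% in step 3.
- At R2 = 30% the planned SE is 1.07-1.14 times the true SD. Putting these into 2[1 − Φ(1.645 × ratio)] gives 7.8% and 6.1%, in line with the table.
- The 30% row excludes skewed size (calibration reached only 24%) and counts with correlated baselines.
- A rank ANCOVA with own baseline only, as one possible fallback, gives 8.8-9.6%, 7.5-8.8% and 6.6-8.1% at R2 = 10%, 20% and 30%.

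**5. Independent check.** A separate simulation used a normal outcome, correlated baselines, and blocks of 2, blocks of 4 or minimisation. At R2 = 30% the planned type I error was 7.4-8.3%, against 9.0-10.1% with all four variables. The SE fell from about 0.317 to 0.272 SD, which is 1 − 0.272/0.317 = 14%. Under simple randomisation the planned level stayed at about 10%, so the conservatism comes from the balancing.

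**6. If balancing fails** (simple 20:20): type I error is 9.7-10.1%, and the power change is −0.7 to +0.8 points at R2 = 10% and +4.0 to +9.9 at 30%.

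**7. Household rule.** The number of same-household pairs and their intraclass correlation (ICC) are assumptions. Clustering alone, with 3-10 pairs and ICC 0.3-0.5, gives a type I error of 10.8-14.5%. The table combines clustering with balancing (normal outcome, ICC 0.4, 5,000 runs, Monte Carlo SE 0.4-0.5 points).

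| Pairs | Planned, R2 = 10% / 20% | All four, R2 = 10% / 20% |
|---|---|---|
| 3 | 9.6% / 9.3% | 10.4% / 11.2% |
| 6 | 10.6% / 10.4% | 11.7% / 12.2% |
| 10 | 11.1% / 11.7% | 12.1% / 12.8% |

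A further, smaller run with 3-6 pairs put the planned model at about 9-13%.

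**The case against.** The strongest reply is that own-baseline ANCOVA is a valid pre-specified model, that this is a pilot with no stated power to contradict, and that every magnitude rests on an R2 the documents do not supply. That stands, and it sets the weight at minor. At R2 = 10% the gain is small, and nil if balancing also fails. Lesion number and size are probably correlated, so each may add little given the other. The 60% to 71% example is a favourable case: gains are smaller for counts and sizes, and some of those settings are missing at R2 = 30%. The sponsor's choice of balancing variables suggests that it thinks they matter, but does not show it.

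A reader might infer something stronger: that the planned test is conservative overall, so that the plan carries no false-positive risk. The documents do not support this. Section 9 keeps households together and Section 14 has no household term. Step 7 shows that this can cancel or reverse the conservatism if several households enrol. The type I figures in step 4 isolate the covariate omission and do not describe the trial's error rate.

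The opposite inference, that the omission itself inflates type I error, also fails: in steps 4 to 6 the planned model stays at or below about 10% within simulation error.

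**Conclusion.** The mismatch between Sections 2 and 9 and Sections 13 and 14 is in the current text. Its consequence is conditional. If the omitted variables are prognostic beyond the endpoint's own baseline, the plan forgoes precision, worth about 0 to 12 power points over the assumed R2 range of 10-30%. The associated conservatism needs working balance and applies to this omission alone. If the variables are not prognostic, nothing is lost by leaving them out. The size rests on assumed R2, effect size, allocation algorithm and 1:1 ratio. Severity is minor: this is an efficiency point in a small pilot, not a validity flaw.

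Two details in Sections 9 and 12 are separate clarifications and lend this point no support: the overlapping mucosa cut, which may be a typing or conversion error, and the missing rule for combining the two arch scores.

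**What to change.** In Section 14, pre-specify all four balancing variables as main-effect covariates in every model, continuous where possible, using the Baseline values recorded for allocation. Continuous entry stays well defined if the cut points are moved.

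- Number model: own baseline plus lesion size, mucosa and age.
- Size model: own baseline plus lesion number, mucosa and age.
- Mucosa model: pre-challenge Baseline mucosa score as own baseline, since no post-challenge score is scheduled, plus lesion number, lesion size and age.

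Keep the treatment-by-baseline interaction check to the endpoint's own baseline. Align the Section 13 wording.

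The cost is wording, plus three residual degrees of freedom: 37 to 34 with 40 completers, 31 to 28 with 34. If the variables are not prognostic, power for 0.6 SD falls by 1.1-2.3 points with 40 completers and 1.5-2.9 with 34. No new data are needed. The change does nothing about household clustering and removes slack that may partly offset it (step 7), so the household rule should be considered alongside it.

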Continuance criteria will be assessed, and subjects will be asked to complete a questionnaire. Subjects will be asked to remove their mandibular and maxillary full dentures and the dentures and subjects' mouths will be cleaned by a dental professional if applicable. An OST will be performed followed by a Mucosa Condition Assessment and then a pre-peanut challenge Gum Abrasion Evaluation.

Subjects will then be asked to eat 20 grams of peanuts 4 times for a total consumption of 80 g of peanuts (subjects will be permitted to take breaks if needed and drink small sips of water). Additionally, subjects will be timed for each peanut challenge. If subjects are unable to finish the peanuts due to being too full or for any other reason, this will be noted in the eCRF General Comments. After completion of the peanut challenge, subjects will have a post-peanut challenge Gum Abrasion Evaluation. Subjects will be reminded to refrain from eating approximately 4 hours prior to next visit.

Week 4:

Continuance criteria will be assessed, and subjects will be asked to complete a questionnaire. Subjects will be asked to remove their mandibular and maxillary full dentures and the dentures and subjects' mouths will be cleaned by a dental professional if applicable. An OST will be performed followed by a Mucosa Condition Assessment and then a pre-peanut challenge Gum Abrasion Evaluation.

Subjects will then be asked to eat 20 grams of peanuts 4 times for a total consumption of 80 g of peanuts (subjects will be permitted to take breaks if needed and drink small sips of water). Additionally, subjects will be timed for each peanut challenge. If subjects are unable to finish the peanuts due to being too full or for any other reason, this will be noted in the eCRF General Comments. After completion of the peanut challenge, subjects will have a post-peanut challenge Gum Abrasion Evaluation. Subjects will return their kit boxes and will be dismissed from the study.

General Comments and Adverse Events, if applicable, will be recorded. Subject Accountability will be recorded as subjects are dismissed from the study at any point.

2020089

3. Inclusion Criteria

In order to be included in the study, each subject must:

1. Be 18 years of age;
2. Read, sign, and receive a copy of the Informed Consent prior to initiation of study procedures;
3. Have a full maxillary and mandibular denture and wear on a daily basis;

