4. Have a history of food particles getting under their full denture and causing gum irritation;
5. Are willing to abstain from eating at least four hours prior to the visits;
6. Are willing to eat 4 X 20 grams of peanuts three times (Baseline, Week 2 and Week 4) without denture adhesive;
7. Clean their dentures on a daily basis;
8. Agree not to change their regular denture cleaning routine;
9. Agree to abstain from using denture adhesive during the study;
10. Agree to not participate in any other oral/dental product studies during the study.

4. Exclusion Criteria

Subjects are excluded from study participation if they:

1. Exhibit evidence of obvious oral pathology, as determined by the Study Dentist, as a result of a mandatory OST examination on the first day of the study;
2. Are allergic to any of the ingredients contained in the study product gel;
3. Are allergic to peanuts;
4. Wear dentures overnight;
5. Are insulin-dependent and/or have any health condition(s) which would prevent compliance with study procedures;
6. Are routinely using denture adhesive;
7. Present with any disease or conditions that could be expected to increase their susceptibility to gum abrasion (like diabetes or xerostomia); or
8. Present with any disease or conditions that could be expected to interfere with examination procedures or the subject's safe completion of the study.

5. Continuance Criteria

Subjects may be excluded from the study or the analysis if they:

1. Become intolerant to study procedures;
2. Develop insulin dependence and/or any health condition(s) which would prevent compliance with study procedures;
3. Did not abstain from eating at least four hours prior to the visits;
4. Have their denture altered during study;
5. Use denture adhesive;
6. Change their denture cleaning routine;
7. Wear their denture overnight;
8. Develop any disease or conditions that could be expected to increase their susceptibility to gum abrasion (like diabetes or xerostomia); or
9. Are non-compliant with the protocol.

6. Identity of Investigational Product(s)

- **Control:** Current Denture Care
- **Treatment:** Current Denture Care + Treatment Gel

7. Product Usage

Control Group:

Evening denture care:

2020089

In the evening subjects will perform their regular denture cleaning routine (if subjects brush their oral mucosa with brush, they will be allowed to continue doing so). They will be instructed to sleep without dentures.

Treatment Group:

Evening denture care:

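### The Week 2 and Week 4 prevention outcomes are all taken before that visit's peanut challenge, so prevention while eating peanuts has no prespecified direct test

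*Combined protocol and SAP*

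**What the plan says.** Section 1 gives the aim as to "evaluate the effectiveness of denture gel at treating and preventing gum abrasions while eating peanuts".

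Section 2 schedules the 80 g challenge at Baseline, Week 2 and Week 4, and adds: "Following the peanut challenge, a licensed dental professional will re-evaluate the number and size of abrasions". The Week 2 and Week 4 visit descriptions repeat this: "After completion of the peanut challenge, subjects will have a post-peanut challenge Gum Abrasion Evaluation". They place the mucosa score before the peanuts: "An OST will be performed followed by a Mucosa Condition Assessment and then a pre-peanut challenge Gum Abrasion Evaluation". At Baseline, treatment is assigned only after the challenge: "Next subjects will be randomized to one of two treatments balanced on their baseline post-peanut challenge gum abrasion evaluations".

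Section 13 states a prevention hypothesis for number, size and mucosa over Weeks 2 and 4. It calls the Baseline covariate post-challenge but does not say whether the Week 2/4 outcome is taken before or after the peanuts.

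Section 14 does say. Its prevention paragraph opens "To assess the impact of the product on the prevention of lesions, the average size of the Pre-challenge Abrasions (in mm", then names the pre-challenge number and the mucosa score. These are analysed by repeated-measures ANCOVA with the Baseline post-challenge value as covariate. The by-week analyses concern the same responses, and the optional size categories are also pre-challenge. A general clause allows further exploratory analysis without naming an outcome, visit or model.

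**The concern.** The study repeats a controlled challenge twice on treatment and records its effect, but no specified model takes that effect as its outcome. One of the two stated aims is left to indirect evidence.

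A gel that protects the mucosa only during the challenge could leave the planned prevention tests close to null. A gel that only reduces everyday lesions, or only speeds healing, could make them positive. The post-challenge data will exist in either case. With no outcome named for them, the definition of prevention could be chosen after the results are seen.

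**Working it through.** **Trace of the outcomes.** No figure in the plan needs reproducing: Section 10 sets 40 subjects for logistical reasons and gives no effect size, SD or power. The check is where each evaluation is used.

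| Evaluation | Use in the plan |
|---|---|
| Baseline post-challenge | Balancing and stratification (Sections 2, 9); covariate (Sections 13, 14) |
| Days 3 and 6 (no challenge) | Treatment outcomes |
| Weeks 2 and 4, pre-challenge number and size | Prevention outcomes |
| Weeks 2 and 4, mucosa score (before the peanuts) | Prevention outcome |
| Weeks 2 and 4, post-challenge number and size | No specified analysis |

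So 3 of 3 prevention outcomes precede that visit's challenge. Up to 40 × 2 = 80 on-study post-challenge evaluations are collected at Weeks 2 and 4, and none is a prespecified outcome.

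**Timing.** Randomization and product distribution follow the Baseline challenge, so the Week 2 pre-challenge value precedes any challenge on gel. The Week 4 pre-challenge value comes 4 − 2 = 2 weeks after the only earlier one.

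**How much challenge effect reaches the planned outcome.** Let a challenge cause on average *c* new lesions in Control and *c*/2 with gel, with no effect on everyday lesions. Let a share *f* of Week 2 challenge lesions persist to Week 4 in both groups. The group difference is then:

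- pre-challenge number: 0 at Week 2 and *f* × 0.5*c* at Week 4, with two-visit mean 0.25*fc*;
- post-minus-pre change: 0.5*c* at each visit, with mean 0.5*c*.

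The ratio is 0.25*fc* / 0.5*c* = *f*/2: nothing at *f* = 0, 12.5% at *f* = 25%, and 25% at *f* = 50%.

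**Illustrative rejection rates (number of abrasions).** Taken from the plan: 40 subjects, two-sided 10%, ANCOVA with the Baseline post-challenge covariate. Assumed:

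- 20 subjects per arm with complete data;
- gamma-Poisson counts with subject CV 0.5;
- Baseline post-challenge mean 1.6, borrowed from the adjustable cut point in Section 9;
- everyday mean 0.2 to 0.8, with the rest of the 1.6 due to the challenge;
- no merging of lesions.

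The model is an ANCOVA of the two-visit mean. Ranges in the first row run over the everyday mean at 25% carry-over; the second row also spans carry-over of 0 to 50%.

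| Gel effect | Pre-challenge | Total post-challenge | Post-minus-pre change |
|---|---|---|---|
| Halves challenge lesions only | 11-16% | 33-73% | 64-81% |
| Halves everyday lesions only | 16-65% | 11-33% | about 10% |
| Healing only (25% rather than 50% persist) | 13-27% | 11-13% | 10-11% |

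With no effect at all, at least one of the three definitions rejects in 18-21% of runs, against 10% for one outcome. Counting only rejections that favour the gel, the figure is about 10% against 5%.

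**The case against.** The best defence is that pre-challenge status is what the sponsor means by prevention. The gel is applied in the evening and left overnight. Inclusion criterion 4 requires subjects to "Have a history of food particles getting under their full denture and causing gum irritation", so everyday lesions and tissue condition are sensible outcomes. Section 14 uses the pre-challenge label consistently. This stands as far as it goes: the planned analyses answer a legitimate question and should stay. It does not remove the mismatch with Section 1, which ties the aim to eating peanuts.

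A reader might infer the opposite, that the label is a drafting slip. The prevention paragraph closely follows the treatment paragraph, where Days 3 and 6 have no challenge and no post-challenge value was possible. The documents do not settle this either. Section 13 leaves the point open.

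The exploratory clause permits a post-challenge analysis but specifies none.

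The simulated rates can be challenged, and rightly. They rest on assumed inputs and do not cover the non-parametric fallback in Section 14. They also ignore merging: if 30% of existing lesions merged at the challenge (everyday mean 0.8), the change in number would lose power, from 64% to 35% for a gel that halves both kinds of lesion. It would also reject 14% of the time for a gel that acts on everyday lesions only, nearly always against the gel. The figures therefore do not establish change in number as the only defensible lead outcome.

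**Conclusion.** The point holds on the text alone. As written, the prevention tests measure everyday lesions, residual healing and tissue condition, and not the response to the Week 2 and Week 4 challenges. The *f*/2 result needs only the stated assumptions on effect and persistence; the rejection rates are illustrations.

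Four stronger readings go too far:

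- **The prevention analysis is invalid or uninformative.** It is informative about daily life and only indirect for the challenge.
- **Choosing afterwards gives an 18-21% chance of a false claim of benefit.** That range includes rejections against the gel. The favourable share is about 10% instead of 5%, so the doubling is real but the level is lower. The plan also states its 10% per test and labels additional analyses exploratory.
- **Unfinished challenges in Control would create spurious benefit.** If Control subjects alone ate less, they would tend to have fewer challenge lesions, and false rejections would run almost entirely against the gel.
- **Stated power is lost.** None is stated.

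This should be fixed. It is not fatal in a pilot sized for logistical reasons.

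**What to change.** Before unblinding, amend Sections 13 and 14:

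1. Add a Week 2/4 prevention analysis of the post-challenge abrasion evaluations, in the same repeated-measures ANCOVA (or the plan's non-parametric alternative) with the Baseline post-challenge covariate.
2. Name one challenge-response outcome for the prevention claim and label the others supporting. Candidates are the same-visit post-minus-pre change, or the post-challenge value adjusted for the same-visit pre-challenge value. Each has a weakness to weigh: a change in number is sensitive to merging lesions, and the adjusted value conditions on a measurement taken after randomization that the gel may have altered.
3. Keep the pre-challenge and mucosa analyses, labelled everyday prevention and tissue condition, and state that they are not alternative routes to the same claim.
4. Tabulate incomplete challenges by group. Keep all randomized subjects with both evaluations in the lead analysis. Repeat it without incomplete challenges as a sensitivity analysis only, because completion is observed after randomization.

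If pre-challenge status was the intended meaning of prevention, say so and reconcile Section 1 with Sections 13 and 14 instead.

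The cost is wording, one derived outcome and one completion flag per challenge, with no new visit or measurement. The downsides are one more outcome to rank, and a response that depends on the amount eaten. The plan records a shortfall only as free text: if a subject is "unable to finish the peanuts due to being too full or for any other reason, this will be noted in the eCRF General Comments".
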